6.8 Concomitant Therapy

Any medication or vaccine (including OTC or prescription medicines, recreational drugs, vitamins, and/or herbal supplements) or other specific categories of interest that the patient is receiving at the time of enrollment or receives during the study must be recorded along with:

[figure not shown]
- a. reason for use
- b. dates of administration including start and end dates
- c. dosage information including dose and frequency

The Medical Monitor should be contacted if there are any questions regarding concomitant or prior therapy before the Investigators initiate the therapy.

6.8.1 Permitted Medications

Permitted medication includes anti-malarials nonsteroidal anti-inflammatory drugs including selective cyclooxygenase-2 inhibitors at approved dosage, low dose oral corticosteroids (prednisone \leq 10 mg/day or equivalent); methotrexate \leq 25 mg PO or SC weekly concomitantly with folic acid or folinic acid.

6.8.2 Prohibited Medications

Prohibited medications may include, but are not limited to, those listed in [Appendix 6](#) (Section 10.6). These listings of prohibited concomitant treatments are not considered all inclusive. If the use of these types of medications is medically necessary during the course of the study, the Investigator must contact the Sponsor Medical Monitor to discuss further administration of TCK-276. A decision to allow the patient to continue in the study will be made on a case-by-case basis.

6.8.2.1 Caution

Investigators should recognize potential interactions with these drugs and avoid maximum doses, if possible, if these drugs are used. Cautioned medications may include, but are not limited to, those listed in [Appendix 6](#) (Section 10.6). These listings of cautioned concomitant treatments are not considered all inclusive.

7 Discontinuation of Study Intervention and Patient Discontinuation

7.1 Discontinuation of Study Intervention

It may be necessary for a patient to permanently discontinue study intervention. If study intervention is permanently discontinued, the patient will remain in the study to be evaluated for clinical observation and safety monitoring. See the SoA ([Table 1-1](#)) for data to be collected at the

time of discontinuation of study intervention and follow-up and for any further evaluations that need to be completed.

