- Treatment duration: Up to 11 days (Day -1 to Day 10)
- Visit frequency: Screening Visit, Days -1 to 10 Visits; Follow-up/end of treatment (EOT) Visit. Following discontinuation of TCK-276, patients will be followed unless they withdraw their informed consent for study participation.

Number of Patients:

A total of 32 patients with RA are planned for enrollment and randomized into 4 cohorts with 8 patients per cohort. Within each cohort, 6 patients will be randomized to TCK-276 and 2 patients will be randomized to matching placebo.

Note: “Enrolled” means a participant’s, or their legally acceptable representative’s, agreement to participate in a clinical study following completion of the informed consent process and Screening. Potential participants who are screened for the purpose of determining eligibility for the study, but do not participate in the study, are not considered enrolled, unless otherwise specified by the protocol. A participant will be considered enrolled if the informed consent is not withdrawn prior to participating in any study activity after Screening.

Intervention Groups and Duration:

This MAD study will consist of 4 cohorts of 8 patients (6 active treatment and 2 matching placebo, or a 3:1 ratio), each receiving an oral dose of TCK-276 or matching placebo for 7 days (QD under fed condition). The first cohort will be divided into 2 subgroups to implement the sentinel dosing approach. Within the cohort, the first subgroup will consist of 2 sentinel patients;

one patient will receive TCK-276, and one patient will receive matching placebo. The second subgroup will consist of 6 patients (5 active treatment, 1 matching placebo). Individual patients in the second subgroup will be dosed at least 72 hours after the first dose of the second sentinel patient of the first subgroup following a decision by the Investigators based on all available safety data from the sentinel patients up to 48 hours post-dose. Subsequent cohorts (cohort 2-4) will not include the sentinel dosing approach.

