7.2 Patient Discontinuation/Withdrawal from the Study

A patient may withdraw from the study at any time at their own request or may be withdrawn at any time at the discretion of the Investigator for safety, behavioral, or compliance reasons. The patient will be permanently discontinued from the study intervention and the study at that time.

If the patient withdraws consent for disclosure of future information, the Sponsor may retain and continue to use any data collected before such a withdrawal of consent.

If a patient withdraws from the study, he/she may request destruction of any samples taken and not tested, and the Investigator must document this in the site study records.

At the time of discontinuing from the study, if possible, an early discontinuation visit should be conducted, as shown in the SoA ([Table 1-1](#)). Refer to the SoA for data to be collected at the time of study discontinuation and follow-up and for any further evaluations that need to be completed.

In addition to the stopping rules described in Section [7.1.1](#), a patient will be withdrawn by the Investigator or designee from the study and not be allowed to continue with the study if any of the following criteria are fulfilled:

- Any patient who develops an AE \geq Grade 3 (CTCAE version 5.0).

- Patient will be discontinued from further dosing if following toxicities are observed:
 - Hematologic: Neutropenia, absolute neutrophil count < 1000/mm³, hemoglobin < 9 g/dL, white blood cell < 2.5 × 10³/µL
 - Renal: serum creatinine > 3 × ULN
 - Hepatic: bilirubin elevation > 2 × ULN; AST or ALT elevation > 3.0 × ULN
 - QTcF prolongation: mean QTcF ≥ 500 ms or change from the nearest baseline > 60 ms
 - ECG abnormalities including ventricular tachycardia or ventricular fibrillation, complete heart block (Grade III atrioventricular block) or second degree atrioventricular block Mobitz type II
 - Hypertension: resting systolic BP ≥ 180 mmHg and ≤ 80 mmHg diastolic BP
Hypotension: resting systolic BP ≥ 110 mmHg and ≤ 40 mmHg diastolic BP
 - Pulse (resting) < 35 or > 110 bpm
- A patient may withdraw from the study at any time at his/her own request or may be withdrawn at any time at the discretion of the Investigator for safety, behavioral or administrative reasons.
- If the patient withdraws consent for disclosure of future information, the Sponsor may retain and continue to use any data collected before such a withdrawal of consent.

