- If a patient withdraws from the study, he/she may request destruction of any samples taken and not tested, and the Investigator must document this in the site study records.
- Withdrawn patients may be replaced if patient withdrawal is not due to safety or tolerability reasons.
- Refer to the SoA for assessments to be performed at the time of study discontinuation.
 - At the discretion of the Investigator or designee, the patient may continue with study assessments after discontinuation until the final Follow-up Visit procedures are performed. A reasonable effort will be made to determine the reasons why a patient fails to return for the necessary visits or is discontinued from the study. If the patient is unreachable by telephone, a registered letter, at the minimum, should be sent to the patient requesting him/her to contact the study center.

While patients are encouraged to complete all study evaluations, they may withdraw from the study at any time and for any reason. Every effort will be made to determine why any patient withdraws from the study prematurely. All patients who withdraw from the study with an ongoing AE must be followed until the event is resolved or deemed stable. If a patient withdraws prematurely after dosing, all data to be collected prior to discharge from the clinical site should be collected at the time of premature discontinuation or at the scheduled discharge.

Patient participation may be terminated prior to completing the study and the reason recorded as follows:

1. Adverse event
2. Protocol violation
3. Loss to follow-up
4. Patient withdrew consent at own request
5. Other

A genuine effort must be made to determine the reasons why a patient fails to return for the necessary visits or is discontinued from the study. If the patient is unreachable by telephone, a registered letter, at the minimum, should be sent to the patient requesting him/her to contact the clinic.

Patients who are withdrawn after randomization for non-drug-related reasons may be replaced following discussion between the Investigator and the Sponsor. Patients withdrawn after randomization as a result of AEs thought to be related to the study drug will generally not be replaced.

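### Section 7.2 withdraws from the study any patient with a Grade 3 or higher AE, contradicting 7.1 and the synopsis and making scheduled safety days before Day 14 discretionary

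*Protocol*

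**What the plan says.** Two places in the protocol keep a patient who stops drug under observation. Section 7.1 states: "If study intervention is permanently discontinued, the patient will remain in the study to be evaluated for clinical observation and safety monitoring". The synopsis (1.1) states: "Following discontinuation of TCK-276, patients will be followed unless they withdraw their informed consent for study participation".

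Section 7.2 goes the other way. Its lead-in says that "a patient will be withdrawn by the Investigator or designee from the study and not be allowed to continue with the study" if a listed criterion is met. The first criterion begins "Any patient who develops an AE" and sets the threshold at CTCAE Grade 3 or above. It has no relatedness condition and no end day. The second criterion, a list of toxicities under the same lead-in, is worded differently: "Patient will be discontinued from further dosing if following toxicities are observed".

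Section 7.2 also contains safeguards:
- "All patients who withdraw from the study with an ongoing AE must be followed until the event is resolved or deemed stable".
- After a premature withdrawal following dosing, the data "to be collected prior to discharge from the clinical site should be collected at the time of premature discontinuation or at the scheduled discharge".
- "At the discretion of the Investigator or designee, the patient may continue with study assessments after discontinuation", up to the final follow-up procedures.

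Section 4.1 brings every patient back on Day 14, including early terminators. Section 8.4.1 ends AE collection at Day 14 or at the early termination visit.

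**The concern.** For a Grade 3 or higher AE, 7.1 and 7.2 give opposite instructions. Reading 7.1 as a rule about drug and 7.2 as a rule about the study does not reconcile them. Section 7.1 has no patient-level criteria of its own, and 7.1.1 covers stopping of the study or a cohort. The patient-level safety criteria are in 7.2, under a study-withdrawal lead-in, so the follow-up promised in 7.1 is overridden for the patients with the most severe events. Once the Day 7 dose has been given, withdrawal prevents no further dosing and can only reduce observation.

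Safety and tolerability are the primary objective. The SAP summarises laboratory values and vital signs by time point (4.13.3, 4.13.4). It leaves repeat, retest and unscheduled values out of summary statistics (4.2.5) and does not impute missing results (4.17). Off-schedule clinical follow-up would therefore not fill the missed time points, and later summaries could describe mainly the patients who tolerated the drug.

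**Working it through.** The plan states no figure on this point, so the check is a count of scheduled days.

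**Inputs (protocol Table 1-1 and footnotes)**
- Last dose: Day 7 (footnote 10).
- Laboratory days: 4 and 7 (footnote 4), then 8, 9, 10 and 14. The Day 1 sample is taken before dosing (footnote 1), so it is baseline.
- ECG days: 1 and 7 (footnote 8), then 8, 9, 10 and 14.
- Vital-sign days: each of Days 1 to 10, then 14.
- Active patients per dose group: 6.

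**Denominator.** Post-baseline laboratory days per patient are 4, 7, 8, 9, 10 and 14, which is 6. Then 6 patients × 6 days = 36 active laboratory patient-days per dose group.

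**Rule as written.** The Day 14 visit is kept (4.1). One pre-discharge set is taken, either at withdrawal, where it restores no later time point, or at the scheduled Day 10 discharge, where it restores Day 10. Assessments on the withdrawal day itself are taken as done, and the Investigator is assumed not to continue the others.

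| Withdrawal day | Scheduled days after it and before Day 14 | Set taken at withdrawal: lab / ECG / vital signs lost | Set taken at Day 10: lab / ECG / vital signs lost |
|---|---|---|---|
| 4 | lab and ECG 7, 8, 9, 10; vital signs 5–10 | 4 / 4 / 6 | 3 / 3 / 5 |
| 7 | 8, 9, 10 for each | 3 / 3 / 3 | 2 / 2 / 2 |
| 8 | 9, 10 for each | 2 / 2 / 2 | 1 / 1 / 1 |
| 9 | 10 for each | 1 / 1 / 1 | 0 / 0 / 0 |
| 10 or later | none | 0 / 0 / 0 | 0 / 0 / 0 |

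**Laboratory loss from one affected patient, as a share of the dose group**
- Day 4: 4/36 = 11.1%, or 3/36 = 8.3%.
- Day 7: 3/36 = 8.3%, or 2/36 = 5.6%.

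At each missed time point the patient is 1 of 6 on active drug.

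**What the safeguards cover.** Follow-up of ongoing AEs (7.2), of abnormal laboratory values (8.3.5), and of SAEs and AESIs (8.4.3) concerns the event or the abnormal value. None of it makes the scheduled series mandatory between withdrawal and Day 14. The only clause that reaches those days is the discretionary one in 7.2.

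**The case against.** The strongest reply is that little is lost in practice. The triggering event is recorded, graded and followed. Section 8.4 makes the Investigator responsible for following AEs that are serious, related or the cause of stopping drug, and 8.3.4 requires hourly ECG and continuous monitoring after a clinically significant telemetry change. Section 7.2 refers to the same schedule of activities as 7.1 and lets the Investigator continue assessments to the end. The summaries are descriptive, no hypothesis is tested, all laboratory data are listed, and clinically significant abnormalities appear as AEs. Discretion is also reasonable for a patient who may need care elsewhere.

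Most of this stands, and it limits the weight of the point. It does not remove the contradiction, and it does not make the intervening days mandatory. SAP 4.2.5 would not exclude scheduled assessments continued under the discretion clause, so the loss is possible, not certain. The post-dose case is small but not empty: an AE after the Day 7 morning dose still puts three days of each assessment at risk, or two if the Day 10 set is taken.

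A reader might infer more than the documents support:
- **That Day 14 is lost too.** This would raise the laboratory loss to 5/36 = 13.9% after Day 4 and 4/36 = 11.1% after Day 7, but only if the site ignored both the Day 14 return in 4.1 and the pre-discharge collection in 7.2.
- **That new AEs go unrecorded.** AEs are elicited by questioning (8.4.2) and can be asked about on Day 14. They are missed only if the early-termination cut-off in 8.4.1 is applied over 4.1.
- **That every listed toxicity forces study withdrawal.** That bullet speaks of stopping dosing, which agrees with 7.1. Only its position under the withdrawal lead-in makes it ambiguous.
- **That escalation or stopping decisions change.** Those rules act on the triggering events, which are still counted.

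**Conclusion.** The point holds, at moderate weight. For Grade 3 or higher AEs, 7.2 contradicts 7.1 and the synopsis, whatever the cause and even after the last dose. The consequence is that scheduled laboratory, ECG and vital-sign days between withdrawal and Day 14 are no longer required. By-visit safety summaries could then omit patients with severe events; they need not, because the Investigator may continue assessments.

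The sizes are per affected patient. They rest on the Day 14 return and the pre-discharge set being honoured and on the discretion not being used. The loss falls quickly with the day of withdrawal and is nil from Day 10. The documents give no expected rate of Grade 3 or higher AEs, so no study-level frequency is claimed.

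**What to change.** In 7.2:
- Make a Grade 3 or higher AE a criterion for discontinuing study drug only.
- Move the listed toxicities out from under the study-withdrawal lead-in, since they are already worded as stopping dosing.
- State that scheduled safety assessments continue through Day 14, in-house or as an outpatient where clinically feasible, unless consent is withdrawn.

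As a clarification, align 8.4.1 so that AE collection runs to the Day 14 return that 4.1 already requires.

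The cost is protocol wording plus a continued stay or extra visits for the few affected patients. The clinical thresholds stay as the sponsor set them, and the SAP needs no change.

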7.1.1 Overall Study Stopping Criteria

The study will be stopped if any of the following occur and are thought to be at least possibly related to study intervention agreed upon by the SRC:

- Two patients develop the same Grade 3 AE (grading is based on the Common Terminology Criteria for Adverse Events [CTCAE] version 5.0).
- One patient develops \geq Grade 4 AE (CTCAE version 5.0).
- Death of a patient at any time.

If any of the following scenarios occur within a cohort with reasonable possibility of a causal relationship with study drug, dosing will be stopped, and further dosing will not be initiated.

- One or more patients experience increased alanine ALT or AST $> 3 \times$ ULN with total bilirubin (TBL) $> 2 \times$ ULN or increased AST $> 3 \times$ ULN accompanied by alkaline phosphatase (ALP) $> 1.5 \times$ ULN.
- One or more patients experience a decrease of absolute neutrophil count less than 1,000/mm³ or white blood cell (WBC) less than $2.5 \times 10^3/\mu\text{L}$ or platelet count less than 75,000/ μL .
- One or more patients have an increase of more than 60 ms in QTcF compared to the baseline QTcF (baseline QTcF = value obtained on Day 1 at pre-dose in the treatment period) or QTcF > 500 ms or other clinically significant conduction disturbance or arrhythmia. All ECGs for this determination must be performed under strict resting conditions.
- Two or more patients, who receive study intervention, have tachycardia defined as resting supine heart rate > 125 beats per minute (bpm) persisting for at least 10 minutes.
- Two or more patients, who receive study intervention, have symptomatic bradycardia defined as resting supine heart rate < 40 bpm accompanied with symptoms of bradycardia while awake persisting for at least 10 minutes.
- Two or more patients, who receive study intervention, develop hypertension defined as an increase in resting supine systolic blood pressure (BP) > 40 mmHg to above a reading of 180 mmHg and persisting for at least 10 minutes.

If the criteria were met, the SRC will carefully review the totality of data, considering moderate non-serious AEs at least possibly related to the study intervention administration in unblinded

fashion, the number of patients in which they occur, concurrency of more than one within the same patient. Although changes from normal ranges are most relevant, changes from baseline measurements will also be considered observing any trends. If consensus among the voting SRC members cannot be reached, then the Principal Investigator, who has the ultimate responsibility for the safety of the patients, will make the final decision.

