5.2 Exclusion Criteria

Patients who meet one or more of the following criteria will not be considered eligible to participate in the clinical study:

1. Female patients who are breastfeeding or have a positive urine pregnancy test either at the Screening Visit or at Admission.
2. Patients who are unable to eat the prescribed meals during the stay at the site; vegetarian or vegan.
3. Patient has a history of significant drug allergy, as determined by the Investigator.
4. Patient has used a study drug, any prohibited medication(s) (see Section 6.8.2), over-the-counter (OTC) medications, vitamins, dietary and herbal supplements within 14 days or 5 half-lives if known (whichever is longer) prior to the first dose of study drug.
5. Patient has a history of active suicidal ideation in the past 6 months prior to the Screening Visit, or any psychiatric disorders that will affect the patient's ability to participate in the study as determined by the Investigator.
6. Patient has a current or recent (within 14 days prior to the Screening Visit) history of uncontrolled, clinically significant infectious, hematological, renal, endocrine, pulmonary, gastrointestinal, cardiovascular, hepatic, psychiatric, neurologic, or allergic disease.
7. Patient with any of the following laboratory abnormalities either at the Screening Visit or at Admission. These assessments may be repeated once at the discretion of the Investigator.
 - a. Aspartate aminotransferase (AST), alanine aminotransferase (ALT) \geq 2 times the upper limit of normal (ULN)
 - b. Bilirubin \geq 1.5 times ULN
 - c. An estimated glomerular filtration rate (eGFR) according to Cockcroft-Gault \leq 60 mL/min
 - d. Hematology values below the lower limit of normal: Neutropenia, absolute neutrophil count $<$ 1000/mm³, hemoglobin $<$ 9 g/dL, white blood cell $<$ 2.5 \times 10³/ μ L
 - e. Clinically significant abnormalities, as judged by the Investigator
8. Patient has a history of alcohol and/or drug abuse within 24 weeks of the Screening Visit.
9. Patient has positive results for drug testing either at the Screening Visit or at Admission.
10. Patient has positive breath alcohol test either at the Screening Visit or at Admission.

11. Regular consumption of alcohol within 6 months prior to the Screening Visit

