7.1.2 Dose Escalation

After each sub-cohort and cohort, the Principal Investigator and the SRC will evaluate the safety, tolerability data and available PK data up to Day 10 to determine the next dose. The predefined AUC_{tau} [REDACTED] level will be used in the SRC as a benchmark so that the human exposure can be compared with preclinical exposure data. The safety and PK data from all patients in the previous cohort must be reviewed before a decision to escalate the dose can be made. Dose escalation will only occur if data from a minimum of 6 patients have been reviewed from the previous lower dose group, such that data from a minimum of 4 patients who have received active treatment will be used to make the dose escalation decision (based on the randomization of 6 active treatment:2 matching placebo).

Doses will not exceed a dose level at which the geometric mean of AUC_{tau} exceeds or would be anticipated to exceed the following limits:

[REDACTED]

[REDACTED]
[REDACTED]
[REDACTED]
[REDACTED]

If PK data indicate that the predefined AUC [REDACTED] has been achieved or would be exceeded with escalation to the next higher dose, dose escalation will be stopped. A dose in which the stopping criteria have been met will not be repeated and further dose escalation will not occur. Where stopping criteria have not been met, the decision of the SRC may be to give the next intended dose, a smaller than the predefined dose increment, a repeated dose or to stop dosing. The SRC will make the decision for the next dose level (to give the next intended dose, a greater or smaller dose increment than the intended dose, a repeated dose) or whether to stop the study after reviewing all the pertinent safety and any other relevant data and decision of the voting members. If consensus among the voting SRC members cannot be reached then the Principal Investigators, who have the ultimate responsibility for the safety of the patients, will make the final decision on the next dose level or whether to stop the study. In any event, dose escalation can only occur if agreed by the Principal Investigators. The decisions of the SRC on the next dose level will be documented and provided to all the appropriate parties

involved with the study, including the pharmacist to enable study intervention preparation for the next scheduled dosing day.

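### The one-patient liver stop for a cohort omits ALT from its ALP limb, so a possibly drug-related ALT > 3 × ULN with ALP > 1.5 × ULN does not by itself stop dosing

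*Protocol*

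**What the plan says.** Protocol Section 7.1.1 has two groups of rules. The first stops the study on CTCAE grade or death. The second acts when a listed event occurs "within a cohort with reasonable possibility of a causal relationship with study drug, dosing will be stopped, and further dosing will not be initiated". The liver item in the second group needs only one patient and has two limbs:

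- **Bilirubin limb:** "One or more patients experience increased alanine ALT or AST" > 3 × ULN, together with total bilirubin > 2 × ULN.
- **ALP limb:** AST > 3 × "ULN accompanied by alkaline phosphatase (ALP") > 1.5 × ULN. ALT is not named.

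Meeting a criterion has two further consequences. Section 7.1.1 continues: "If the criteria were met, the SRC will carefully review the totality of data". Section 7.1.2 adds: "A dose in which the stopping criteria have been met will not be repeated and further dose escalation will not occur".

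The protocol sets transaminase thresholds in two other places, and both name both enzymes. Exclusion criterion 7a in Section 5.2 ("Aspartate aminotransferase (AST), alanine aminotransferase (ALT"), at ≥ 2 × ULN) governs entry. Section 7.2 ("AST or ALT elevation" > 3.0 × ULN) ends dosing for the individual patient. The SAP has no liver stopping rule; its Section 4.13.10 only describes the Safety Review Committee (SRC).

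**The concern.** Two mirror-image liver profiles get different treatment, and the visible text gives no reason. Suppose causality is judged reasonably possible in both. A patient at ALT 2, AST 5, bilirubin 1, ALP 2 (all × ULN) stops the cohort. A patient at ALT 5, AST 2, bilirubin 1, ALP 2 does not.

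The second patient stops dosing under Section 7.2 either way. The exposure is to the other patients in the cohort, who may go on receiving the same dose. The pattern also fails to set off the SRC review that follows a met criterion, or the bar on repeating the dose and escalating.

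Cohorts 2 to 4 have no sentinel pair (Section 4.1), so predefined cohort stops carry more of the protection at the higher doses.

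**Working it through.** The plan states no operating characteristic for this rule, so there is no figure to reproduce. The check is a logical enumeration.

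**Inputs (Section 7.1.1).** Four yes/no conditions: ALT > 3, AST > 3, total bilirubin (TBL) > 2, ALP > 1.5, all × ULN. Causality is taken as reasonably possible throughout.

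**Rules compared.**

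- As written: [(ALT or AST) and TBL] or [AST and ALP].
- With ALT added: (ALT or AST) and (TBL or ALP).

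**Result over the 2⁴ = 16 combinations.** Each cell shows as written → with ALT added.

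| Raised transaminase | Neither TBL nor ALP | TBL only | ALP only | Both |
|---|---|---|---|---|
| Neither | no → no | no → no | no → no | no → no |
| AST only | no → no | stop → stop | stop → stop | stop → stop |
| ALT only | no → no | stop → stop | **no → stop** | stop → stop |
| Both | no → no | stop → stop | stop → stop | stop → stop |

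- As written: 0 + 3 + 2 + 3 = 8 of 16 stop.
- With ALT added: 0 + 3 + 3 + 3 = 9 of 16 stop.
- The single difference is ALT > 3, AST ≤ 3, TBL ≤ 2, ALP > 1.5.
- In the ALP-only column with at least one raised transaminase, 2 of 3 cells stop as written and 3 of 3 with ALT added.
- Exchanging ALT and AST changes the answer in 2 cells as written and in none with ALT added.

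These are counts of cells, not probabilities.

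**Is it a matter of reading the sentence?** Grouping it instead as (ALT or AST) and [TBL or (AST and ALP)] gives the same answer as the first reading in all 16 cells. The gap does not depend on how the second *or* is parsed.

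**Consistency.** Of the four transaminase thresholds (exclusion 7a, the two limbs of Section 7.1.1, and Section 7.2), three name both enzymes. Only the ALP limb does not.

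**What else could catch the pattern?**

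| Safeguard | Acts on | Needs |
|---|---|---|
| 7.2, ALT > 3.0 × ULN | that patient only | one result |
| 7.1.1 study stop | whole study | one related Grade ≥ 4 AE, or "Two patients develop the same Grade 3 AE" |
| 7.1.2 escalation stop | next dose, not current dosing | one patient with a related Grade ≥ 3 AE, or two at Grade ≥ 2 in one category |
| 4.1, 7.1.2, 8 | patient, dose level or study | judgement of the investigator, sponsor, Medical Monitor or SRC |

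None of these uses the ALT and ALP pair. The documents do not list CTCAE cut-offs for ALT, so ALT multiples are not converted to grades here.

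**The case against.** The strongest reply is that little exposure is left.

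- **The patient and the next dose are covered.** The affected patient stops on ALT alone. Escalation needs SRC review of safety data from all patients in the cohort and the Principal Investigators' agreement, and Section 7.1.2 allows unblinding for a safety concern. This stands. It confines the gap to other patients finishing the same dose, or that dose being repeated, when nobody uses discretion.
- **Few doses are in play.** Table 1-1 schedules laboratory draws during dosing only on Days 4 and 7 after the Day 1 pre-dose sample, and Day 7 is the last dose. This also stands. For patients dosed in parallel, a Day 4 result available before the next dose could spare at most the three doses of Days 5 to 7. A patient not yet started could be spared all seven, and one who has finished none. Stagger and laboratory turnaround are not stated, so this is a range and not an estimate.
- **One related Grade 4 event already stops the study.** Correct, so the missing stop matters only below Grade 4.
- **A reason may exist in text we cannot see.** In the public copy, Table 2-1 shows only the SARS-CoV-2 row, and the Investigator's Brochure is not available. The missing rationale is therefore weak evidence, and the conclusion does not rest on it. The wording of the rule is visible.
- **The listed events of special interest include no hepatic item, and an extra trigger can end escalation.** Both are fair. But the protocol already accepts a one-patient stop for AST with ALP, at the same cost. Nothing visible supports treating ALT with ALP as less serious.

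**Conclusion.** The concern holds. As written, one combination of the 16 escapes the one-patient cohort stop: ALT > 3, AST ≤ 3, bilirubin ≤ 2 and ALP > 1.5 × ULN. No other rule supplies an equivalent automatic stop for the cohort unless the event reaches Grade 4 or the same related Grade 3 event occurs in two patients.

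The finding is narrow. It concerns co-enrolled patients rather than the affected one, and SRC review after the cohort remains. Its frequency cannot be given from the documents. It assumes that causality is judged reasonably possible and that the rule is applied as worded. The phrasing of the bilirubin limb ("One or more patients experience increased alanine ALT or AST") suggests loose drafting, so the omission may be unintended, but the documents do not say. It is worth a one-line correction to a hard safety rule.

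**What to change.** In Section 7.1.1, reword the second liver limb so that ALT or AST > 3 × ULN, accompanied by ALP > 1.5 × ULN, stops dosing. If AST alone is intended, say why in that section.

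**Cost.** This is a one-line amendment with no new sampling: ALT, AST and ALP are all in Table 10-1.

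The real cost is a small added chance that one result ends escalation under Section 7.1.2. On the four-cohort plan, a trigger in cohort k closes 4 − k higher cohorts of 8 patients:

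| Trigger in cohort | Higher cohorts closed | Patients not enrolled |
|---|---|---|
| 1 | 3 | 24 |
| 2 | 2 | 16 |
| 3 | 1 | 8 |
| 4 | 0 | 0 |

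Background elevation is possible. Methotrexate and NSAIDs are permitted, entry allows ALT just under 2 × ULN, and Section 5.2 sets no numeric ALP limit. Two of every eight patients receive placebo. The permitted drugs and the absence of an ALP limit bear equally on the existing AST limb. The causality condition still applies, and Section 7.1.1 provides for SRC review, with unblinding mentioned, once a criterion is met.
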